Review of Related Literature:

Acne Vulgaris is the eighth most prevalent disease in the world, affecting 9.4% of the global population.⁷ In adults, acne prevalence ranges from 50-54% in females and 40-42.5% in males.^{8,9} Acne is commonly misunderstood to affect primarily teenagers; however, a large proportion of individuals continue to suffer from acne or acquire new onset acne far after their adolescent years.⁸ Up to 64% of individuals have acne persisting into their 20s, and 43% have acne persisting into their 30s.² Moreover, the prevalence of acne did not substantially decrease until after the age of 44.⁹

Safe and effective long-term maintenance therapy is necessary in order to address the chronic and persistent nature of acne.⁵ In the last 3 decades, there has been a significant increase in resistance to antibiotics commonly used to treat acne. This was measured by the increased minimal inhibitory concentration (MIC) against *Propionibacterium acnes* for antibiotics such as erythromycin and tetracycline in patients receiving long-term antibiotic treatment. Increase in MIC was not found in acne patients who were not on antibiotic therapy and in non-acne patients.^{5, 10} This is a significant international public health concern because aside from increase in pathogenic *P. acnes*, resistance can occur in other bacteria more dangerous than *P. acnes*.

Given this situation and the complexity of the repercussions of this trend, it is a challenge to maximize the use of non-antimicrobial therapy when treating acne.^{5,11-14}

The development of a variety of skin disorders, including acne, has been linked to oxidative status. Oxidative stress can be measured using plasma levels of catalase (CAT), superoxide dismutase (SOD), total antioxidant capacity (TAC), and malondialdehyde (MDA). MDA, a marker for oxidative stress, was found to be higher in acne patients compared to controls. TAC together with the antioxidant enzymes, SOD and CAT, were lower for patients with acne. These results suggest that oxidative stress appears to play a major role in the pathogenesis of acne.¹⁵

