Zinc is found in all body tissues. In skin, it is five to six times more abundant in the epidermis than in the dermis. Zinc is an essential element for cell health and proper bodily functions like glandular, reproductive, immune, and neuropsychiatric processes since the conformity, stability and activity of more than 200 metalloenzymes are affected by zinc. Its antioxidant properties have numerous benefits from protection against ultraviolet rays and oxidative damage by decreasing reactive oxygen species (ROS) to improvement of wound healing and prevention of cancer and cardiovascular disease.^{6,16}

Data suggest that zinc deficiency exist both in developed and developing countries, and several factors may affect the serum zinc levels, which include low intake of highly absorbable zinc in fresh foods, and high phytate content of some staple food, pregnancy, lactation, increased demands of physiological processes such as growth and sexual maturation.¹⁷ Whole blood zinc levels were measured from healthy subjects in relation to sex and age using atomic absorption spectrophotometry. Mean level of zinc obtained in whole human blood from males was 607.0 +/- 105.3 micrograms/100 ml and in females 585.2 +/- 122.9 micrograms/100 ml. The results showed that males had slightly higher zinc levels but the difference was not statistically significant.¹⁸ Zinc deficiency starts at 66 micrograms/dL for non-pregnant females and 70 micrograms/dL for males greater than 9 years old.¹⁹

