- To study the relationship between whole blood zinc levels and the severity of acne vulgaris in Filipino patients 18-25 years old and normal controls

SPECIFIC

- To describe the clinical profile of Filipino patients 18-25 years old with acne vulgaris

- To determine the whole blood zinc levels of acne patients compared to controls
- To determine the relationship of the clinical severity of acne vulgaris to whole blood zinc levels

Research Hypotheses:

Null Hypothesis: There is no relationship between whole blood zinc levels and the severity of acne vulgaris.

Alternative Hypothesis: There is a relationship between whole blood zinc levels and the severity of acne vulgaris.

METHODOLOGY

Study Design

A cross-sectional comparative study design will be utilized for this study which will be conducted from November 2017 to March 2018.

Study Setting

The study will be conducted at the Dermatology Out-patient Clinic of the East Avenue Medical Center (EAMC). The hospital has adequate staff and infrastructures to provide for the blood extraction of this study to be conducted properly. Laboratory services of Hi-Precision Diagnostics will be used for measuring whole blood zinc levels for this study.

Study Population

The participants of the study will include patients clinically diagnosed with acne vulgaris, aged 18-25 years of age.

Inclusion Criteria for Cases

- Filipino patients, aged 18-25 years old
- Diagnosis of Acne Vulgaris
- Able to read and write in English or Tagalog
- Seen at the Dermatology Out-Patient Department or Skin Center of East Avenue Medical Center

Exclusion Criteria for Cases

- Patients with other chronic dermatoses or systemic disease
- Taking oral supplements or medications for the past 3 months
- Patients who are pregnant or lactating

Inclusion Criteria for Controls

- Filipino patients, aged 18-25 years old
- Able to read and write in English or Tagalog
- Seen at the Dermatology Out-Patient Department or Skin Center of East Avenue Medical Center

[figure not shown]
Exclusion Criteria for Controls

- Patients with Acne Vulgaris or other chronic dermatoses or systemic disease
- Taking oral supplements or medications for the past 3 months
- Patients who are pregnant or lactating

Study Procedure

1. The study will be submitted to the Technical Review Board and Institution Ethics and Review Board for approval.

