2. In the Dermatology Out-Patient Department of East Avenue Medical Center, patients seeking consult for their skin lesions which were diagnosed to be Acne Vulgaris will be screened if they meet the inclusion/exclusion criteria.
3. Informed consent will be obtained for those who are qualified.
4. Patients will be given proper treatment whether they agree to participate or not. For the patients who agree to participate, the investigator will assess the patient's acne severity using the Global Acne Grading Scale (GAGS).
5. Twelve milliliters of blood will be extracted from the patient with proper aseptic technique and waste disposal.
6. Blood sample will be properly stored in three EDTA tubes, labelled, and transported to the laboratory for determination of whole blood zinc levels through ashing acid digestion-inductively coupled plasma (ICP) using Shimadzu ICPS-7510, an inductively coupled plasma emission spectrometer.
 - a. Blood samples are viable and stable for 5 days at 15-25 degrees Celsius.
 - b. A memorandum of agreement between the principal investigator and Hi-Precision Diagnostics, Inc. has been made. Hi-Precision Diagnostics will be providing the materials for extraction, picking-up, and transporting the blood sample using a special insulated medical specimen bag (Versapak Pathology and Specimen bag) with ice packs and thermometer to help maintain the ideal temperature of 15-25 degrees Celsius.
 - c. Schedule of specimen pick-up is from 8:00 am- 8:00 pm and may be done on an as-needed basis. The blood specimens will be stored in the refrigerator immediately after extraction.
7. Results will be obtained by the investigator via the online results portal of the laboratory.
8. Data collected will be tabulated and data analysis will be done.

Study Framework/Process

Ethical Considerations

The protocol will be submitted for ethical review and approval by the Technical Review Board and Institutional Ethics and Review Board of the East Avenue Medical Center. Informed consent will be obtained from the participants prior to participation in the study. All data collection will be done in a setting that ensures patient safety and privacy. Patient will be assured of the confidential nature of the patient-provider interactions. Active listening, open-ended questions and clarifications will be used.

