
In order to compare the whole blood zinc levels between cases and controls, independent T-test will be used. ANOVA will be used to compare the whole blood zinc levels by acne severity. Multiple linear regression analysis will then be performed in order to determine the association of whole blood zinc levels with acne severity after controlling for the effects of significant confounding variables. All p values ≤ 0.05 will be considered as significant.

CONCLUSION

The correlation of whole blood zinc levels with severity of acne vulgaris in Filipino patients may help clinicians recommend more detailed dietary advice and add non-antibiotic supplements to their current treatment of acne vulgaris. The results of the study can serve as a guide for

further studies related to whole blood zinc and its role in the pathogenesis of acne vulgaris in Filipino patients.

Key Words: Whole Blood Zinc, Acne Vulgaris, Filipino

REFERENCES:

1. Aydemir EH. Acne vulgaris. *Turk Pediatri Ars*. Mar 2014;49(1):13-6. doi:10.5152/tpa.2014.1943
5. Humphrey S. Antibiotic resistance in acne treatment. *Skin Therapy Letter*. 2012;17(9):1-3.
6. Prasad AS. Zinc is an Antioxidant and Anti-Inflammatory Agent: Its Role in Human Health. *Frontiers in nutrition*. 2014;

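### The acne-versus-control comparison has only an unadjusted t-test assigned to it; a sex- and age-adjusted estimate would be a cheap, minor improvement

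*Combined protocol and SAP*

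**What the plan says.** Under Objectives, the second specific objective reads "To determine the whole blood zinc levels of acne patients compared to controls". The Plan of Data Analysis in the SAP assigns it one method: "In order to compare the whole blood zinc levels between cases and controls, independent T-test will be used". ANOVA is then given to the comparison by severity. Multiple linear regression is given to the "association of whole blood zinc levels with acne severity after controlling for the effects of significant confounding variables". The confounders are not named, and the plan does not state whether controls are in that regression.

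Under Study Population, two inclusion lines appear in the same words for cases and for controls: "Filipino patients, aged 18-25 years old" and "Seen at the Dermatology Out-Patient Department or Skin Center of East Avenue Medical Center". Both groups also exclude recent oral supplements or medications, pregnancy or lactation, and other chronic dermatoses or systemic disease. Neither list mentions sex, and no matching or stratification is described.

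The Review of Related Literature gives mean whole blood zinc of 607.0 (SD 105.3) micrograms/100 ml in males and 585.2 (SD 122.9) in females, adding: "The results showed that males had slightly higher zinc levels but the difference was not statistically significant". It also reports acne prevalence by sex: "In adults, acne prevalence ranges from 50-54% in females and 40-42.5% in males".

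**The concern.** Acne patients and controls are self-selected groups, so a raw difference in mean zinc can partly reflect who is in each group. The plan accepts this for severity, where it adjusts, but assigns no adjustment to the case-control objective. Sex is the one factor for which the protocol itself reports differences both in zinc and in acne frequency. In the quoted figures, women have the lower zinc mean and the higher acne prevalence, so any sex bias would push towards lower zinc in acne, the direction reported by the earlier studies the protocol cites. The Significance of the Study section says that a significant relationship could be used as evidence for giving zinc supplements, so it is reasonable to ask that a raw group difference not stand alone.

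**Working it through.** **The plan's own figure.** No power or precision is given for the t-test. The only power statement is for the four-group ANOVA: lambda = 40 × (13.30/20.00)² = 17.69, with 3 and 36 df and alpha 0.05, gives 93.2% against the stated 95%. The present point does not rest on that figure.

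**Inputs.** Zinc means and SDs by sex, and acne prevalence by sex, come from the Review of Related Literature. Group sizes come from the Justification of Sample Size: 10 each of mild, moderate and severe acne, so 30 cases, and 10 controls. Assumptions: the source population is half male, the two SDs are pooled with equal weight, and the test is two-sided at 0.05 (the plan does not state sidedness).

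**Step 1: sex gap and standard error** (100 ml = 1 dL).
- Gap = 607.0 − 585.2 = 21.8 micrograms/100 ml.
- SD = √((105.3² + 122.9²)/2) = 114.4, so the gap is 21.8/114.4 = 0.19 SD.
- SE of the case-control difference = 114.4 × √(1/30 + 1/10) = 41.8.

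**Step 2: imbalance implied by the prevalences.** With female prevalence pF and male prevalence pM, the male share is pM/(pM + pF) in people with acne and (1 − pM)/(2 − pM − pF) in people without.
- Smallest sex contrast (pF 50%, pM 42.5%): 0.425/0.925 = 45.9% against 0.575/1.075 = 53.5%, a gap of 7.5 points.
- Largest sex contrast (pF 54%, pM 40%): 0.40/0.94 = 42.6% against 0.60/1.06 = 56.6%, a gap of 14.1 points.

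**Step 3: bias = imbalance × 21.8.** The false-positive rate is from the noncentral t with 38 df.

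| Sex imbalance | Bias (micrograms/100 ml) | Bias in SE | False-positive rate |
|---|---|---|---|
| 7.5 points | 1.6 | 0.04 | 5.0% |
| 14.1 points | 3.1 | 0.07 | 5.1% |
| 30 points | 6.5 | 0.16 | 5.3% |
| 60 points | 13.1 | 0.31 | 6.1% |
| 100 points | 21.8 | 0.52 | 8.0% |

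The last three rows are illustrations, not forecasts.

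**Step 4: cost of adjusting.** Adding sex and age takes the residual df from 38 to 36, and the critical t from 2.024 to 2.028.

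**The case against.** The strongest defence is that confounding is already limited by design. Restriction is a standard control, and both groups are confined to Filipinos aged 18-25 from the same clinics, with the same exclusions for supplements or medications, pregnancy or lactation, and systemic disease. An unadjusted comparison followed by an adjusted regression is also an ordinary sequence. The research question sets severity against normal controls, and the sample-size text makes controls one of the four ANOVA groups, so the regression may include them and yield adjusted contrasts. Most of this stands, and it is why the point is minor. It does not close the gap: sex is left free, the plan does not say that controls enter the regression, and a severity model would not necessarily give a single acne-minus-control estimate.

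A reader might be tempted to go further in four ways that the documents do not support.

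- **Clinic.** Step 2 of the Study Procedure refers to screening "In the Dermatology Out-Patient Department of East Avenue Medical Center, patients seeking consult for their skin lesions", while the control criteria also allow the Skin Center. But the case criteria carry the identical clinic line. This is a loose end in the procedure, not a planned difference between the groups.
- **No balancing at all.** The shared eligibility criteria contradict this. Age in particular can differ only within 18-25.
- **Chance imbalance with 10 controls.** Random imbalance in sex is already part of the t-test's sampling error. It does not bias the test.
- **A markedly inflated false-positive rate.** Reaching one needs either an unnamed factor with an assumed strength, or the sex gap set against the planning SD of 20.00 (14% at a 30-point imbalance). The planning SD is stated in mg/dL and cites a study whose title concerns serum, whereas the whole blood SDs in the protocol are 105.3 and 122.9. Diet is a plausible factor, since the protocol lists low intake of absorbable zinc and phytate as influences on serum zinc. The plan describes no collection of dietary data, however, and adjusting for sex and age would not remove such a bias.

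**Conclusion.** The point holds in a limited form. The case-control objective is assigned only an unadjusted test in non-randomised groups that are not balanced on sex, and the plan is silent on whether the adjusted model covers controls. On the protocol's own figures the expected sex bias is 1.6-3.1 micrograms/100 ml, or 0.04-0.07 standard errors, and the test's error rate barely moves. That rests on a half-male source population, on the quoted prevalences applying to this clinic, and on the quoted whole blood means and SDs applying to these participants. The protocol reports the sex difference itself as not statistically significant. The t-test is therefore not shown to be invalid. The gain from adjusting is real but small. Severity: minor.

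**What to change.** In the Plan of Data Analysis, make the main estimate for the second specific objective the acne-minus-control difference, with its 95% confidence interval, from a linear model of whole blood zinc on group (acne or control), with sex and age as prespecified covariates kept in the model whatever their p-values. Report the unadjusted difference and t-test beside it. State also whether controls enter the severity regression.

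The change takes a sentence or two and needs no new visit or test. Age is needed for the eligibility check, and sex is known at screening. The statistical cost is the 2 degrees of freedom shown above.
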